5.2 Dose Limiting Toxicity

The Dose Limiting Toxicity (DLT) will be defined as any of the following events which are at least possibly attributed to APX005M and occur during the first 2 courses (6 weeks, 42 days) following the APX005M administration. Management and dose modifications associated with adverse events are outlined in Section 6.

Management and dose modifications for toxicities which occur outside of the dose-finding period should also follow section 6; however these will not be considered dose limiting for the purpose of dose escalation.

5.2.1 Dose-Limiting Toxicities (DLT's)

- Any APX005M-related adverse event during the first 2 courses of therapy (6 weeks, 42 days) that leads to a dose reduction or results in the permanent cessation of therapy will be considered dose limiting. All dose modifications in all courses are to follow the guidelines provided in Section 6.2.
- Any APX005M-related adverse event during the first 2 courses of therapy that results in a delay of treatment > 2 weeks.

5.2.1.1 Non-hematologic dose limiting toxicity is defined as:

- Any grade 4 non-hematologic toxicity
- Any grade 3 non-hematologic toxicity with the exception of:
 - Grade 3 nausea and vomiting < 5 days
 - Grade 3 diarrhea responding to optimal medical treatment within 5 days
 - Grade 3 elevation of transaminases that returns to levels meeting eligibility criteria within 7 days of study drug interruption and does not recur upon restarting drug.
 - Grade 3 fever or infection of fewer than 5 days in duration

- Grade 3 hypophosphatemia, hypokalemia, hypocalcemia or hypomagnesemia that are asymptomatic and responsive to oral supplementation
- Grade ≥ 3 cytokine release syndrome
- Toxicity related to treatment with APX005M which delays scheduled re-treatment for > 2 weeks, or >1 week for cytokine release related complications.

5.2.1.2 Hematologic dose limiting toxicity is defined as:

- Any grade 4 hematologic toxicity with the exception of lymphopenia
- Grade 3 neutropenia with fever
- Grade 3 thrombocytopenia on 2 separate days or requiring a platelet transfusion on 2 separate days within a 7 day period.

5.2.2 Dose-finding period

The dose finding period begins with the initial dose of APX005M and ends on the last day of course 2, which is 6 weeks (42 days) in duration. Should there be a delay starting the subsequent course, dose finding will complete on the start date of the subsequent course. The recommended phase 2 dose (RP2D) will be based on the MTD and the totality of the safety/efficacy data.

5.2.3 Dose Escalation/ De-escalation

Dose escalations/de-escalation decisions will be based on the 3+3 design as described in the statistical section of the protocol. The initial cohort of three (3) patients will be treated at 0.1 mg/kg (the dose levels to be tested are listed in

Table 2). Only DLTs observed during the dose-finding period of therapy will be used to guide dose escalation/de-escalation.

5.3 Concomitant Medications and Supportive Care Guidelines

5.3.1 Steroids

Corticosteroids should be used at the lowest dose to control symptoms of edema and mass effect, and discontinued, if possible. Use of corticosteroids should be recorded in the PBTC-051 database.

5.3.2 Anticonvulsant drugs

Anticonvulsant drugs should be used, if indicated. Use of anticonvulsants should be recorded in the PBTC-051 database.

5.3.3 Growth Factors

Routine use of growth factors (e.g., G-CSF, GM-CSF and erythropoietin) is not permitted. However, therapeutic use of G-CSF or GM-CSF in patients with serious neutropenic conditions, such as sepsis, may be considered at the investigator's discretion. Use of growth factors should be recorded in the PBTC-051 database.

5.3.4 Anti-emetics

The use of anti-emetics will be at the investigator's discretion. Use of anti-emetics should be recorded in the PBTC-051 database. Steroid should not be used as anti-emetics.

5.3.5 Febrile neutropenia

Febrile neutropenia should be managed according to the local institutional guidelines.

5.3.6 Neurosurgical or other surgical procedures

If a neurosurgical procedure or other surgical procedure is required for a reason other than tumor progression (i.e. the onset of hydrocephalus), these procedures should be documented, but will not constitute criteria for declaring the patient “off therapy”. APX005M should be held until the patient is clinically stable and has recovered from the acute effects of surgery.

5.3.7 Live vaccines NOT allowed

Examples of live vaccines include, but are not limited to, the following: measles, mumps, rubella, varicella, yellow fever, rabies, BCG, and typhoid (oral) vaccine. Seasonal influenza vaccines for injection are generally killed virus vaccines and are allowed; however, intranasal influenza vaccines (e.g. Flu-Mist®) are live attenuated vaccines, and are not allowed.

5.4 Duration of Therapy

In the absence of treatment delays due to adverse event(s) or disease progression, treatment may continue for 36 courses (approximately 2 years) or until one of the Off Treatment Criteria applies noted in section 5.4.2.

Patients will be followed weekly during the first 2 courses and prior to course 3 – 36 till the end of therapy, and at the time of disease progression or completion of treatment. The medical history, physical exam (including height, weight, vital signs, and performance status), dates of drug administration, adverse events, neurologic exam, relevant laboratory evaluations, and routine neuro-imaging scans will be assessed. Disease assessment studies should be uploaded if required per protocol (Section 9.2) Please review Section 10 of the protocol for the required assessments and intervals.

If the patients are tolerating APX005M and non-progressive at 2 years, the patients may request to continue non-protocol APX005M treatment from Apexigen.

5.4.1 On Study Data Submission Schedule

Pre-treatment, on-study and off-treatment data, as well as patient response data are to be recorded in the electronic data collection screens using the PBTC-051 database. See the Required Data and Timetable for Submission form located on the PBTC-051 Protocol webpage for the schedule. For assistance, contact the PBTC Protocol Coordinator listed on the cover page. An optional roadmap is located on the PBTC-051 Protocol Webpage.

5.4.2 Off Treatment Criteria

At the discontinuation of treatment, the “Off Treatment Date” is to be recorded in the eCRF and is to be consistent with the reason given for going off treatment. The “Last Treatment Date” is defined as the last date that the patient received protocol based therapy. Date of “off treatment” must be the greatest of the date of last treatment, date of procedure, date of patient assessment, notification of patient/family decision, or decision made by the physician that resulted in the patient being taken off protocol treatment. The reason for discontinuation of treatment must be documented by the attending investigator in the medical record and recorded in the eCRF.

Patients will be considered Off Treatment for the following reasons:

- Development of unacceptable toxicity as outlined in section 5.2.1. See section 7 for specific reporting requirements.
- Progressive disease (PD) as described in section 11.3.
- Development of a medical or psychiatric illness that in the investigator's judgment renders the patient incapable of further therapy on this protocol or the treating physician determines continuation on this study is not in the patient's best interest.
- The patient, parent or legal guardian refuses further treatment on this protocol. In this case the investigator should clarify if the family also wishes to withdraw consent for continued participation for data collection purposes.
- Completion of all protocol defined treatment
- Pregnancy
- Non Compliance that in the opinion of the investigator does not allow for ongoing participation.

Patients who are off protocol therapy must be followed until an “Off Study Criterion” is met.

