5.1 Agent Administration

5.1.1 APX005M (CD40 agonistic mAb)

APX005M dosing will begin at 0.1 mg/kg, which is one dose level below the adult recommended phase 2 dose. For APX005M, both 1 mg/kg and 0.6 mg/kg were explored in adult participants, and the adverse events at 0.6 mg/kg were manageable and reversible. The APX005M dose will be increased in subsequent cohorts until the MTD is reached or until dose level 3 is complete without MTD being defined (

Table 2). No inpatient dose escalation will be permitted on the protocol. Only DLTs observed during the dose-finding period (the first 2 courses, i.e., the first 6 weeks of treatment) will be used to guide dose escalation. Dose escalation will be governed by the statistical design as described in section 13 of the protocol.

Table 2

Dose Escalation Schedule		
Dose Level	Dose of APX005M (mg/kg, IV, Q3 weeks)	round final dose to
0	0.03 mg/kg	2 decimals
1* (starting dose level)	0.1 mg/kg	1 decimal
2	0.3 mg/kg	1 decimal
2.5	0.45 mg/kg	1 decimal
3	0.6 mg/kg	1 decimal
Note: Dose level 2.5 will only be studied if dose level 3 is deemed to be too toxic.		

Subjects will be assigned a dose level at the time of enrollment. APX005M will be administered at the assigned dose level on Day 1 of each course 21 day. Patients may continue to receive APX005M for 36 courses (approximately 2 years) or until disease progression, unacceptable toxicity or death, whichever occurs first. Delays between courses for reasons other than toxicity may occasionally occur however dosing should follow the treatment plan as closely as possible.

Dosing should be adjusted based on weight (kg) calculated at the beginning of each course of therapy. The dose may be prescribed using the weight that was determined at the prior visit. However, if the current weight is $\geq 5\%$ different from the prior weight, the prescription should be revised.

Accrual to Stratum 1 was completed as of May 14, 2020. Dose level 3 (0.6mg/kg) was determined to be the recommended phase 2 dose for Stratum 1. The starting dose for Stratum 2 (the DIPG cohort) was set to be one dose level below the RP2D determined in the non-DIPG patients (Stratum 1) (also see Section 13.1.3). Therefore, accrual to Stratum 2 was initiated at dose level 2 (0.3mg/kg). Accrual to Stratum 2 remains open at the time of this amendment.

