6.2 Hematologic and Non-hematologic Adverse Events and Management

6.2.1 Dose Modifications for Hematologic Toxicity

Dose adjustments are based on nadir blood counts since the preceding administration of investigational product.

If a patient experiences dose-limiting hematological toxicity as outlined in Section 5.2.1.2, APX005M treatment will be reduced to the next lower dose level. If the toxicity resolves to meet on study parameters within 14 days of drug administration, provided there is no current active bleeding in the case of dose-limiting thrombocytopenia, the patient may resume therapy at one dose level lower. Patients who are dose-reduced for toxicity will not have their dose re-escalated. If toxicity does not resolve to meet on study parameters within 14 days of drug administration, the patient must be removed from protocol therapy. Two dose-reductions per patient are allowed. If any dose-limiting toxicity occurs in a patient already dose-reduced twice for toxicity, the patient must be removed from protocol therapy. APX005M dose adjustments for hematologic toxicity during treatment are described in Table 3.

Table 3: APX005M Dose Modifications for Hematologic Toxicity

APX005M related toxicity	APX005M dose modification
Grade 4 Neutrophil count decrease	Dose reduction
Grade 3 Neutrophil count decrease with fever	Dose reduction
Grade 4 Thrombocytopenia	Dose reduction
Grade 3 Thrombocytopenia on 2 separate days or requiring a platelet transfusion on 2 separate days within a 7 day period	Dose reduction

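### Section 5.4.2 defines off-treatment toxicity by pointing to the DLT list, although Section 6.2 orders dose reduction, not removal, for many of those DLTs

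*Combined protocol and SAP*

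**What the plan says.** Section 5.4 lets treatment run for up to 36 courses "or until one of the Off Treatment Criteria applies noted in section 5.4.2". The first reason listed in 5.4.2 is "Development of unacceptable toxicity as outlined in section 5.2.1". Section 5.1.1 also names unacceptable toxicity as a stopping condition ("or until disease progression, unacceptable toxicity or death, whichever occurs first") and the abstract does the same; neither defines it.

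The section that 5.4.2 points to is the DLT definition, which 5.2 confines to the first 2 courses (42 days). Its first bullet says that a related event in that window "that leads to a dose reduction or results in the permanent cessation of therapy will be considered dose limiting". So the list mixes events that lower the dose with events that end therapy. The same bullet adds: "All dose modifications in all courses are to follow the guidelines provided in Section 6.2". Section 5.2 likewise says: "Management and dose modifications associated with adverse events are outlined in Section 6".

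Section 6.2.1 then gives the action for one part of the same list: "If a patient experiences dose-limiting hematological toxicity as outlined in Section 5.2.1.2, APX005M treatment will be reduced to the next lower dose level". It lets the patient resume one level lower after recovery, allows two reductions, and removes a patient who has a further DLT after two reductions. Tables 3 and 4 set out the action for each toxicity.

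**The concern.** Two operative rules point to the same list and give different actions. Section 5.4.2 treats what is in 5.2.1 as a reason to come off treatment. Section 6.2 treats much of it as a reason to lower the dose and carry on. A site that followed 5.4.2 to the letter during the DLT window could stop APX005M in a child whom Section 6 would keep on the next lower dose, in a population with few other options. The reason for stopping must also be entered in the medical record and the eCRF, so an unclear criterion can carry over into the recorded reason for discontinuation.

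**Working it through.** No sample size or error rate is involved. The check is to match each row of Tables 3 and 4 to the DLT list, and then to ask whether the dose-finding results depend on which reading a site adopts.

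**Step 1. Match the rows (courses 1 and 2).**

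| Row | Action in Section 6.2 | On the 5.2.1 list? | Literal 5.4.2 |
|---|---|---|---|
| Table 3: grade 4 neutropenia | Reduce | Yes (5.2.1.2) | Conflicts |
| Table 3: grade 3 neutropenia with fever | Reduce | Yes (5.2.1.2) | Conflicts |
| Table 3: grade 4 thrombocytopenia | Reduce | Yes (5.2.1.2) | Conflicts |
| Table 3: grade 3 thrombocytopenia, repeated or transfused | Reduce | Yes (5.2.1.2) | Conflicts |
| Table 4: nausea/vomiting, grade 4 or prolonged grade 3 | Reduce | Yes; only grade 3 under 5 days is exempt | Conflicts |
| Table 4: diarrhea, grade 4 or unresponsive grade 3 | Reduce | Yes; only grade 3 that responds within 5 days is exempt | Conflicts |
| Table 4: CRS grade 3, 7 days or less | Reduce | Yes | Conflicts |
| Table 4: CRS grade 3, over 7 days | Discontinue | Yes | Agrees |
| Table 4: CRS grade 4 | Discontinue | Yes | Agrees |
| Table 4: other grade 3 or higher | Decided with study chair | Mostly | Open |

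The CRS rows do not depend on how the bullets in 5.2.1.1 are nested. The first bullet of 5.2.1 makes any related event in the window dose limiting if it leads to a reduction or ends therapy.

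**Step 2. Count.** Table 3: 4 of 4 rows order reduction. Table 4: 3 of 6 order reduction, 2 order discontinuation, 1 is left to discussion. Conflict with a literal 5.4.2: 4 + 3 = 7 of 10. Agreement: 2 of 10. Open: 1 of 10.

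**Step 3. Does the choice of reading change the dose finding?** Take a patient with one of the seven events in courses 1 or 2.

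- If the site reduces the dose, the event is a DLT through the dose-reduction limb of the first bullet.
- If the site stops therapy, the event is a DLT through the permanent-cessation limb.
- A patient removed for toxicity after at least one dose stays evaluable under Section 11.1.1.

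The patient adds 1 to the DLT count and 1 to the evaluable patients either way. The 3+3 decisions and the RP2D do not move.

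**Step 4. Are there stopping rules without 5.4.2?** Yes, and they are not limited to courses 1 and 2:

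- 5.1.2: infusion reaction recurring at the 50% rate.
- Section 6: failure to recover in the allowed time, more than two reductions, or a reduction below dose level 0.
- 6.2.1: failed hematologic recovery, or a DLT after two reductions.
- Table 4: CRS grade 3 for more than 7 days, or CRS grade 4.
- Table 5: grade 4 CRS or infusion reaction.

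**The case against.** The strongest reply is that the protocol rules out the literal reading. Section 5.4.2 speaks of unacceptable toxicity, not of any DLT. If every DLT ended treatment, the dose-reduction limb of 5.2.1 could never apply, 6.2.1 could not order a reduction for the DLTs it names, and its rule removing a patient who has a DLT after two reductions would have almost no use. A site that follows the pointer also lands on a bullet that contains the permanent-cessation limb and sends it to Section 6.2. All of this stands. It settles the intent and keeps the priority low.

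It does not make the pointer correct. No text says that Section 6 prevails over the off-treatment list. The sentence in 5.2.1 governs dose modification. The bullet in 5.4.2 on the patient's best interest adds a reason to stop; it does not permit continuing. The notice to the study chair in Section 6.1 concerns dosage modifications and does not expressly mention discontinuation.

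A second reply also stands: 7 of 10 counts table rows. It measures neither patients nor the chance that a site misapplies the rule.

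A reader might go further and infer that, because DLTs are confined to courses 1 and 2, the protocol has no usable stopping standard from course 3 on. The documents do not support that. Section 5.2 says of later events, "however these will not be considered dose limiting for the purpose of dose escalation", so it excludes them for that purpose only. Section 5.2.1 sends dose modifications in all courses to 6.2. Section 6.2.1 itself uses the DLT thresholds later: with full dose in course 1 and reductions at courses 2 and 3, a DLT after two reductions can occur at the earliest in course 3. The rules in step 4 also apply in any course.

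**Conclusion.** The cross-reference is wrong as written, and the error is minor. During courses 1 and 2 it conflicts with 7 of the 10 rows of Tables 3 and 4, while the intended rule is plain from Sections 5.2, 5.2.1 and 6. What lifts it above pure editing is that 5.4.2 is an operative stopping rule and, followed literally, gives the wrong action.

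The practical reach is small. Stratum 1 accrual is closed, and Stratum 2, open at this amendment, expects about 12 evaluable patients. The documents give no basis for estimating how many patients could be affected. The two DLTs reported in Stratum 1 (2 of 12 evaluable at dose level 3) were grade 3 infusion-related reactions, which do not fall clearly in any of the seven rows, and the documents do not say what was done with treatment afterwards. They are therefore not evidence that the rule was misapplied. Nor should a reader infer that the Stratum 1 RP2D is in doubt; step 3 shows that it does not depend on this wording.

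The conclusion assumes only that some site could read 5.4.2 at face value. Nothing in the documents shows that one has.

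**What to change.** In the first bullet of 5.4.2, replace the pointer to section 5.2.1 so that the reason reads: *Development of unacceptable toxicity requiring permanent discontinuation of APX005M under Section 5.1.2 or Section 6, or any other APX005M-related toxicity for which the investigator, after discussion with the study chair, permanently stops therapy.* The bullet's sentence on reporting under Section 7 stays.

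The last clause is needed. The DLT definition covers any related event in the window that ends therapy for good, whether or not a specific rule required it. Without that clause, such a stop would have to be recorded under another off-treatment reason.

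The cost is one line at the next amendment, with no change to dosing rules, data collection or analysis.

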5.4.3 Data Submission Schedule for Patients Off Treatment

All patients must be followed for a minimum of 30 days from last treatment date. Toxicities that are considered at least possibly related to APX005M and are ongoing at the end of day 30 of last treatment date will be followed until resolution or return to baseline unless consent is withdrawn for further data submission or follow-up.

Patients in long term follow-up (Stratum 2 DIPG patients) will continue to be followed for 3 years from the initiation of protocol treatment to document any unexpected later developing toxicities or other morbidity and to document disease progression and survival. The requested follow-up data, including imaging uploads requested in Section 9.2, are to be submitted quarterly in the RAVE database from the date the patient went off treatment. Data to be recorded during this interval are the following:

- Any adverse events that are possibly, probably or definitely related to APX005M (see Section 7.3 for specific reporting timelines)
- Dates of disease progression
- Date of progression assessments and the associated results
- Date of commencement of new anticancer therapy
- Date of most recent contact
- Date of death

5.4.4 Criteria for Removal from Study

Patients who are off protocol therapy will be followed until they meet criteria for removal from study. The date and reason for the patient coming off study must be documented in the eCRF and the Operations, Biostatistics and Data Management Core (OBDMC) must be notified according to standard reporting guidelines (see section 5.4.3, sections 7, section 12, and the Required Data and Timetable Submission form located on the PBTC-051 protocol webpage).

Ongoing AEs, or AEs that emerge after the patient is removed from protocol therapy but within 30 days of the last dose of study treatment, must be followed and reported via Rave and CTEP-AERS (if applicable). Toxicities that are at least possibly related to the study treatment and are

ongoing at the end of day 30 of last treatment date will be followed until resolution or return to baseline, whichever is longer.

- Patient determined to be ineligible.
 - If the patient was found to be ineligible after starting treatment, follow-up should continue for 30 days from the last administration of study drug.
- Patient did not initiate treatment on study.
- Parent, patient, or guardian withdraws consent for further required observations or data submission.
- Patient death while on study. The IRB, Investigational Drug Branch (IDB), Study Chair and OBDMC must be notified as per section 7.
- Patient has completed study follow-up as defined per 5.4.3.
- Lost to follow-up
 - Sites must make every attempt to continue follow-up of patients during the study period as specified in Section 5.4.1. Multiple attempts must be made and documented to obtain required study data before patient can be declared lost to follow-up. The study Protocol Coordinator and Study Chair must be notified before a subject is declared lost to follow-up.
- DIPG patients treated in Stratum 2 who are removed from treatment for reasons other than withdrawal of consent or death will be followed until death or 3 years from diagnosis, whichever is earlier.

5.4.5 Data Submission for Patients Off study

No data will be collected documenting treatment or reporting events or disease status that occurs subsequent to the official “off study” date with the exception of adverse events with an attribution of possible, probable, or definite that occur after the “off study” date for agents being studied (see section 7).

